## 2 STUDY OBJECTIVES AND PURPOSE

### 2.1 Rationale for this Study

GMI-1070 is a potent, rationally designed glycomimetic inhibitor of E-, P-, and L-selectins *in vitro*. GMI-1070 has been shown to inhibit inflammation in several animal models of disease, including the VOC of SCD. This study drug is being developed for the treatment of VOC in SCD. In the present study, subjects 12 to 60 years of age who are hospitalized for VOC will be evaluated for the efficacy, safety, and PK of GMI-1070.

Amendment 1 expanded assessment of GMI-1070 from adults aged 16 to 45 to adolescents aged 12 to 15 years. As an inherited disease, sickle cell presents early in childhood and patients in all age groups, from infancy through adulthood, experience VOC. Adolescents generally have fewer co-morbidities and lower incidence of chronic pain and opioid narcotic use, such that GMI-1070 may have a greater treatment effect in younger patients experiencing VOC than adults. GMI-1070 has been well-tolerated in clinical trials to date; and based on the mechanism of action no differences in safety or efficacy would be expected in children as compared to adults. Thus, inclusion of adolescent subjects in clinical studies throughout clinical development is a critical component of the program.

Safety and PK data collected in the 2 prior studies of IV GMI-1070 in healthy adults and 1 study in subjects with stable SCD, have demonstrated an excellent safety profile and linear, predictable PK parameters at a range of doses for up to 4 days of treatment. In addition to the human safety data and based on results of GMI's nonclinical testing in juvenile monkeys and rats, GMI believes that assessment in adolescents aged 12 to 15 years would be safe and well-tolerated.

Amendment 2 revised eligibility criteria in response to further review of criteria in similar studies, with the consensus of the study investigators and DSMB Chair. These criteria included changing the upper age limit to 60, limits on previous transfusions and frequency of recent hospitalizations for VOC.

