### **4.2 Inclusion Criteria**

To be eligible for inclusion, each subject must fulfill each of the following criteria at screening, and must continue to fulfill these criteria prior to dosing:

1. 12 to 60 years of age
2. Confirmed diagnosis of sickle cell disease (HbSS or HbS- $\beta^0$ thalassemia)
3. Diagnosis of VOC at the time of enrollment
4. Hospitalized or in process of admission at the time of enrollment
5. Able to receive the first dose of study drug within 24 hours of initial medical evaluation in the Emergency Department/clinic for VOC;
  - Subjects treated as an outpatient within the past 48 hours for the same VOC episode may be enrolled if dosing is also expected within 24 hours of their second (admitting) presentation.
6. Documented and observed written informed consent (and assent, where applicable)

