    - Subjects may be included if treated as an outpatient within the past 48 hours for the same VOC episode
  11. Recent (within the past 90 days) cerebrovascular accident, transient ischemic attack, or seizure
  12. pRBC transfusions in the past 14 days
  13. Systemic steroid therapy within 48 hours prior to enrollment or expectation that therapy may be used during the study (inhaled or topical steroids are allowed)
  14. For those on chronic or long-acting opioids, a change in dose in the past 14 days OR pain requiring medical attention in the past 14 days (change in opioid medication for acute pain in the past 48 hours and directly related to this VOC admission is allowed)

15. Greater than 5 episodes of hospitalization for VOC in the past 6 months (180 days)
16. Medical or psychiatric condition that, in the opinion of the investigator, may pose a risk to the subject for participation or interfere with the conduct or results of the study
17. Currently receiving, or has received within the previous 4 weeks, any other investigational agent
18. Previous administration of GMI-1070
19. Expectation that the subject will not be able to be followed for the duration of the study
20. Pregnant or lactating female; or female of childbearing potential or male unable or unwilling to comply with birth control methods or abstinence during the course of the study
21. Active use of illicit drugs and/or alcohol dependence, as determined by the investigator

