### **8.2.3.2 Secondary Efficacy Analysis**

Comparisons of time to reduced pain score by at least 1.5 out of 10 cm from the baseline value and time to transition to oral pain medications between the active and placebo treatment groups will be presented by Kaplan-Meier plots stratified by treatment group. The survival distribution will be compared by log-rank test. If there is no censoring in these outcomes, the ANCOVA model similar to the analysis for time to resolution of VOC will be used instead.

The effects of study drug on time to readiness for discharge and time to discharge will also be summarized by treatment group and evaluated by ANCOVA model, controlling for sex and age. Time to readiness for discharge as noted by the subject alone, by the physician alone, and by both the subject and physician, will be considered.

The cumulative amount of IV analgesic use (opioid and NSAID) from admission to discharge will be standardized using morphine equivalents. This amount will be compared between active and placebo treatment groups by an ANCOVA model, controlling for age and sex. The hourly IV analgesic usage over time will be modeled longitudinally using a linear mixed model with subject as a random effect and treatment group, time, sex and age as fixed effects.

The intensity of pain as measured by VAS will be analyzed longitudinally using a linear mixed model with subject as a random effect and treatment group, time, sex, age, and baseline pain score as fixed effects.

The differences in percentage of subjects with complications of VOC including acute chest syndrome, transfusion, stroke and death between active and placebo treatment groups will be tested using Mantel-Haenszel Chi-Square test or Fisher's Exact test, depending on the number of subjects with events.

The mean hsCRP value and mean change from baseline value will be summarized at each time point. If the normal ranges are different among sites, the standardized values will be presented. The difference in values between treatment groups will be analyzed using a linear mixed model with subject as a random effect and treatment group, time, sex, age and baseline measurement as fixed effects.

The results from IV antibiotic usage will be presented in listings. ICU stay and transfusion data including frequency, timing related to VOC and diagnosis leading to transfer to ICU (leading to transfusion) will also be presented in listings.

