### **8.3.2 Sample Size**

Evaluable subjects are those who have received at least 1 dose of study medication. Subjects in the evaluable population will be used to determine when an adequate sample size has been achieved.

The study will enroll until a total of approximately 76 evaluable subjects (defined as those who have received at least 1 dose of study medication) have been enrolled. An interim analysis will be done after the first 50 subjects have completed the follow-up day 7 post last dose, to assess safety and efficacy. The efficacy test statistic for this interim analysis will be compared to a critical value corresponding to a 2-sided alpha of 0.005. To control study wise Type I error, an alpha spending approach will be utilized. The final analysis will then compare the test statistic to a critical value corresponding to 2-sided alpha of 0.045. Futility criteria will also be considered; these will be specified in detail in the statistical analysis plan.

A previous pilot study of treatments for pain in SCD showed the mean pain duration in placebo group is 103 hours with a standard deviation of 60 hours. The original protocol sample sizing was done as follows. Assuming that the variances are the same in both groups and anticipating that the study drug will decrease pain duration by 40%, a total of at least 76 subjects (38 subjects each group) will be needed to detect a 40% decrease in VOC resolution and to achieve 83% power with a 2-sided alpha of 0.045.

With the addition of a second dose level, the power calculation for the study has been updated to compare the treatment difference between the placebo group and the pooled active group (ie, both dose levels combined). The sample sizing assumes that the placebo group has a mean pain duration of 103 hours with a standard deviation of 60 hours, and that both groups – placebo and pooled active groups – share a common standard deviation. Anticipating that the placebo and pooled active groups will each have about 38 subjects (ie, the pooled group will have 19 subjects from each of the dose levels) the study will have an 89% power to detect a 43.8% decrease in VOC duration with a 2-sided alpha of 0.045.

The sample size is also expected to provide initial safety and PK conclusions sufficient to contribute to the design of subsequent trials.

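### The ANCOVA of cumulative IV analgesic use adjusts only for age and sex, omitting baseline weight and chronic opioid use, and so probably loses precision

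*Protocol*

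**What the plan says.** Section 8.2.3.2 defines the quantity: "The cumulative amount of IV analgesic use (opioid and NSAID) from admission to discharge will be standardized using morphine equivalents". It then fixes the method and the covariates: "This amount will be compared between active and placebo treatment groups by an ANCOVA model, controlling for age and sex". The companion analysis is similar: "The hourly IV analgesic usage over time will be modeled longitudinally using a linear mixed model with subject as a random effect", with treatment, time, sex and age as fixed effects. The opening of section 8.2.3 adds that site and age enter as sample size permits. No body-size term, prior-opioid term or transformation is named for either analysis.

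The population is wide. Section 4.2 admits subjects "12 to 60 years of age". Exclusion criterion 14 in section 4.3 removes chronic opioid users only under conditions: "For those on chronic or long-acting opioids, a change in dose in the past 14 days OR pain requiring medical attention" within the past 14 days. A subject on a stable chronic regimen can therefore enter. Section 2.1 itself expects opioid use to differ across this range: "Adolescents generally have fewer co-morbidities and lower incidence of chronic pain and opioid narcotic use".

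**The concern.** Total consumption is duration times hourly rate. The hourly rate plausibly depends on body weight and, more strongly, on whether the subject already takes opioids long term. Both are fixed before randomization. Leaving strong baseline predictors out of an ANCOVA moves their variation into the error term and widens the confidence interval for the treatment effect. In a trial of 76, chance imbalance in chronic users between arms also shifts the estimate.

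Amount and duration of IV analgesics is the first clinical-activity endpoint listed in the synopsis, and it would be a main corroboration of a shorter crisis. An imprecise analysis could leave a real reduction unclear.

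**Working it through.** **The plan's own figures (primary endpoint only).** Section 8.3.2 gives 38 per group, SD 60 h and two-sided alpha 0.045, and states that "the mean pain duration in placebo group is 103 hours with a standard deviation of 60 hours".
- SE = 60 × √(2/38) = 13.77 h.
- A 40% decrease is 41.2 h. Power is 83.9% (normal) or 82.8% (noncentral t), against 83% stated.
- A 43.8% decrease is 45.1 h. Power is 89.8% or 89.0%, against 89% stated.

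Both reproduce. Neither concerns the analgesic endpoint, for which no mean, SD or power is given.

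**How much variation chronic use could add.** From the documents, the duration CV is 60/103 = 0.583, squared 0.339. Assumptions: a share p = 0.35 of chronic users at m times the hourly rate, with rate independent of duration.

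CV² due to chronic status = p(1−p)(m−1)² / [1+p(m−1)]²
- m = 2: 0.2275 / 1.35² = 0.125
- m = 4: 0.2275 × 9 / 2.05² = 0.487

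CV of the total, with no other variation in rate, = √[(1+0.339)(1+CV²) − 1]
- m = 2: √0.507 = 0.71
- m = 4: √0.992 = 1.00

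So chronic status alone could raise the CV from 0.58 to between 0.71 and 1.00. Now add a further rate CV of 0.4 to 0.6 between subjects (also assumed). The squared total CV becomes:
- m = 2: 1.507 × 1.16 − 1 = 0.748, or 1.507 × 1.36 − 1 = 1.049
- m = 4: 1.992 × 1.16 − 1 = 1.311, or 1.992 × 1.36 − 1 = 1.709

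The share of variance explained by chronic status is then 0.125/1.049 = 12% to 0.125/0.748 = 17% for m = 2. For m = 4 it is 0.487/1.709 = 29% to 0.487/1.311 = 37%. Age takes up part of this, because chronic use is rarer in adolescents.

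**Power by simulation.** Setting: 38 v 38, 40% reduction, two-sided 0.05, chronic users about 35% of adults at 2-4 times the rate.

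| Model, untransformed scale | Power |
|---|---|
| Age and sex | about 37-60% |
| Plus chronic-opioid status and weight | about 52-68% |

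Within a scenario the gain is about 7-19 points untransformed and 10-25 points on the log scale. It appears with both gamma and lognormal components, so it does not depend on the assumed shape. The levels move by several points with the assumed age mix and residual spread. If chronic users need no more than others, the gain is small.

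**Does changing the scale help by itself?** No covariates, 40% reduction, 38 per arm:

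| Assumed shape of the total | CV | Raw | Log |
|---|---|---|---|
| Lognormal | 0.58 | 97% | 98% |
| Lognormal | 1.0 | 62% | 75% |
| Lognormal | 1.5 | 35% | 53% |
| Gamma | 0.75 | 82% | 72% |
| Gamma | 1.1 | 48-49% | 33% |
| Gamma duration × gamma rate | 1.05 | 55% | 54% |

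The direction depends on the shape. In the lognormal runs without a treatment effect, Type I error on the raw scale was 3.6-4.9% at a nominal 5%.

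**The case against.** The strongest reply is that covariates and scale for a secondary endpoint belong in the SAP, which is not at hand and to which section 8 defers detail. That disposes of any complaint about silence. But the protocol is not silent on covariates: it names age and sex for this analysis, and section 8 says departures from planned analyses are to be documented in the SAP. The stated choice stands unless the SAP changes it. If it does, the point is met.

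Part of the heterogeneity is already handled. Age is in the model. Criteria 14 and 15 remove unstable and very frequent users, and section 5.2 discourages enrolling subjects whose opioid addiction would cloud the endpoints. This limits the loss but does not remove it, since age is a weak proxy for chronic use among adults. It is also true that the protocol lists no defined chronic-user variable, so one must be derived.

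A reader might go further and infer that the raw scale is wrong, that a few heavy users will dominate the result, and that a 40% reduction will probably be missed. The documents do not support this. They give no distribution or CV for the endpoint. Skewness, a zero bound and an SD that rises with the mean also describe the gamma case, where the log analysis loses power. The 40% and 43.8% effects in section 8.3.2 belong to the primary endpoint and were sized as differences in means with a common SD, so they do not argue for a log scale. A difference in mean consumption is a legitimate target.

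**Conclusion.** The point holds as a probable loss of precision from omitting two baseline predictors. It is not an error in any stated figure, and it does not threaten the validity of the test. Under the stated assumptions the loss is about 7-19 points of power on the untransformed scale. It rests on the share of chronic users and on their rate of use, which the documents do not give; with no rate difference it nearly vanishes. That weight and chronic opioid use predict the total is a reasonable expectation, supported by section 2.1 only as far as opioid use differs by age. Right skew is plausible enough to justify a prespecified sensitivity analysis, but not a change of the main scale.

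**What to change.** In section 8.2.3.2, or in the SAP as a documented change:

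- Add baseline weight and baseline chronic or long-acting opioid use (yes/no, as ascertained for exclusion criterion 14) as covariates in the cumulative-amount ANCOVA and in the hourly-usage mixed model.
- Prespecify a supportive log-scale analysis of the total, reported as a ratio of geometric means with its confidence interval. If any total is zero, use a rank-based analysis instead.
- Do not use log(1+x), which depends on the unit. With lognormal totals of mean 100 units and CV 0.9, power was 67% raw against 55% for log(1+x) with 3% zeros, and 65% against 45% with 5% zeros.

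The cost is small. Baseline weight is already measured for dosing (Table 1, section 6.1.3), and opioid status must be established for eligibility, though it needs a clear yes/no definition in the data. With the active groups pooled, residual degrees of freedom fall from 76 − 4 = 72 to 70. The change should be fixed before the review of clinical activity results in the first 50 subjects (section 8.2.7), so that the choice of covariates cannot be questioned afterwards.

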## 8.2.4 Safety Analysis

Assessment of safety is a secondary objective of the study and will be performed on the safety population. Study site and subject age will be included in the analysis as permitted by sample size.

### 8.2.4.1 Adverse Events

All AEs, including SAEs, will be coded using the MedDRA dictionary. Incidence, severity, and relationship to study medication of AEs will be tabulated by treatment group. Comparison of AEs between treatment groups will be made using a Mantel-Haenszel chi-square test or a Fisher's Exact Test. Summaries will be provided for each of the following types of AEs:

- TEAEs
- Treatment-emergent SAEs
- Treatment-emergent SAEs that were reported as "possibly" or "probably" related to study drug
- TEAEs that were reported as "possibly" or "probably" related to study drug
- TEAEs by severity

TEAEs will be defined as those AEs that begin on or after the date/time of study drug administration. Drug-related AEs will include those AEs that are reported by the investigator as possibly or probably related to the study drug. With the exception of the TEAEs by severity summary, all summaries will present the number of AEs and the number and percent of subjects having an AE by system organ class and by specific AE preferred term. The TEAEs by severity summary will only report the number and percent of subjects. For all percentages, the subjects in the Safety population by treatment group will comprise the denominator.

In addition to these summary tables, subjects with treatment-emergent SAEs and subjects who discontinued prematurely due to a TEAE will be presented in separate subject listings. The listings will provide all of the information reported for that AE and will include the length of time from study drug administration to the occurrence of the AE. If any deaths occur in the study, a similar listing of all TEAEs for subjects who died will be provided.

### 8.2.4.2 Disease Related Adverse Events (DRAEs)

Disease related adverse events (DRAEs) are defined as AEs that occur during a subject's participation in the study, but which are expected for the condition (SCD, VOC), and may include:

- anemia (down to Hb  $\geq 5$ )
- elevated WBC count (up to WBC  $\leq 20,000/\text{mm}^3$ )
- unconjugated hyperbilirubinemia
- elevated markers of hemolysis (AST and LDH)

- proteinuria
- hematuria
- hypertension
- VOC-related swelling/erythema/warmth of an extremity
- nausea/vomiting/constipation
- low fever under 101.5° F
- dehydration
- pruritus
- increased somnolence
- fall in reticulocyte count

DRAEs will be reported and analyzed as AEs per study procedures. In addition to the analysis of all AEs per the section above, DRAEs will be analyzed by treatment group.

#### **8.2.4.3 Vital Signs and Laboratory Parameters**

For vital signs and continuous laboratory parameters, the observed value and the change in the value from baseline at each collection point during the hospitalization will be summarized. For categorical laboratory parameters that are collected in terms of abnormal or normal or can be classified into positive or negative results, the number and percent of subjects having values in each category will be presented at each scheduled collection time. For those categorical laboratory parameters that are reported in several descriptive categories (eg, urine color), the number and percent of subjects by each category will be presented. Graphs displaying population trends over time may be produced.

For both vital signs and laboratory parameters, clinically significant results will be listed with relevant subject information for assessment.

#### **8.2.4.4 Physical Examinations**

Significant changes in physical examination over the study visits will be listed by subject and summarized across the study population as appropriate.

#### **8.2.5 Pharmacokinetic Analysis**

Assessment of PK is a secondary study objective and will be performed on the PK population.

PK data from the first 10 subjects receiving study drug was evaluated in a blinded, aggregate population PK analysis using the methods described here. The purpose was to ensure that GMI-1070 plasma concentration levels in SCD patients in crisis are similar to SCD patients not in crisis (GMI-1070-103) and healthy volunteers (GMI-1070-101 and GMI-1070-102). This information resulted in amendment to the protocol with a change in dose level to achieve the originally targeted plasma concentration levels. In addition, the first 10 subjects under 18 years of age

(regardless of dose level) will be similarly evaluated in a blinded aggregate analysis.

An additional, similar analysis of PK data from the first 10 subjects receiving the new dose level, a loading dose of 40 mg/kg followed by 20 mg/kg every  $12 \pm 2$  hours, will be performed to confirm that anticipated GMI-1070 plasma concentration levels are achieved with the new dose level.

All such analyses will maintain the blind for all those involved in the clinical execution of the study, and will be conducted as follows. A PK model was developed using the plasma concentration data from the 3 previous studies. Covariates (eg, body size, age, sex, etc.) will be incorporated if appropriate, and this model will be updated at each interim analysis. This model will then be used to predict the expected plasma concentration profile from the subjects in the present study, incorporating the actual dosing regimen and covariates. Graphics will be used to assess if the plasma concentration values obtained in the new study are systematically larger or smaller than those predicted based on previous studies. If the new population is biased upward or downward, this information will be utilized to confirm or adjust dose, if necessary, for the remainder of the study. Any required changes in dose of study drug will be addressed in an amendment to this study protocol.

At completion of the study, a formal population PK analysis will be performed, using the structural model developed in previous studies (adapting if appropriate based on the data from the new subjects). This model will accomplish the following goals: to determine if the PK parameters in these subjects differ from those in the 2 previous patient populations, to obtain a set of "typical" parameter values for GMI-1070 in sickle cell patients, to determine which, if any, covariates should be considered in dosing future patients, and to guide selection of the optimal dose magnitude and dose interval for future dosing.

PK parameters to be estimated will include:

CL	Total plasma clearance
CL D2	Clearance from the peripheral (non-central compartment)
V 1	Volume of the central compartment
V 2	Volume of the peripheral (non-central compartment)
C min	Minimum observed drug concentration
C max	Maximum observed drug concentration
t max	Time of the maximum drug concentration (obtained without interpolation)
$\alpha$	Apparent distribution rate constant
$\beta$	Apparent terminal elimination rate constant
t 1/2	Apparent elimination half-life, calculated as $\ln(2)/\beta$

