
 
• Pain management and medications 
 
○ Amount and duration of IV analgesics
 
 
 
• Complications of disease 
 
○ Rate of VOC complications
 
 
 
• Biomarkers of adhesion and inflammation 
 
○ Microvascular blood flow using IVM
 
○ Markers of adhesion
 
○ Markers of inflammation
 
○ hsCRP
 
 
 
• Healthcare and resource utilization 
 
○ Time to readiness for discharge (per subject and physician)
 
○ Rate of transfer to Intensive Care Unit (ICU)
 
○ Diagnosis leading to transfer to ICU
 
○ Duration of hospital length of stay
 
○ Oxygen use
 
○ IV antibiotic use
 
○ Number and type of transfusions
 
 
 
	

Protocol Number: GMI-1070-201	Study Drug: Intravenous GMI-1070

Safety
 
 
• Adverse events (AEs) and local tolerability
 
• Dose-limiting toxicity
 
• Disease related adverse events (DRAEs)
 
• Physical examinations
 
• Vital signs
 
• Clinical laboratory testing: complete blood count with differential, platelets, reticulocyte count, alanine transaminase (ALT, SGPT), aspartate aminotransferase (AST, SGOT), bilirubin (fractionated), blood urea nitrogen, creatinine, electrolytes with glucose, lactate dehydrogenase (LDH), and urinalysis
 
 
PK in Plasma and Urine
 
 
• Parameters as compared to data from previous human studies
 
	

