## 6.4 Pharmacokinetics Sampling

Plasma PK samples will be obtained prior to first dose and at 14 different timepoints following the start of the first dose for a total of 15. These timepoints have been selected so as to describe the time course of optimal plasma levels of GMI-1070, samples being obtained more frequently when plasma concentrations are changing rapidly and less frequently when they are changing more slowly. Although 15 different sample timepoints are identified, it is not practical to obtain that many samples from each individual in this target population, as a result of limited venous access and preexisting anemia. Thus, a "sparse sampling" approach, coupled with population PK methods, has been adopted to decrease the number of samples obtained from each subject. Each subject will be sampled 9 times from a pre-determined subset of the complete collection of timepoints. Subjects will be assigned to 1 of 2 sampling groups (Table 8 and Table 9). This approach – sparse sampling coupled with population PK analysis methods – is widely accepted as appropriate for determining PK parameters in clinical studies.

Beginning at the start of the second or third dose, urine will be collected over 12 hours for each subject. A sample of the urine collected will be tested to determine the concentration of GMI-1070. The urine concentration and volume will be used to determine the amount excreted over the collection period.

Samples will be shipped according to the Sponsor's instructions to the bioanalytical laboratory (refer to the Study Reference Manual for contact information). Specific details for sample handling, storage, and shipping may be found in the Study Reference Manual. Once PK testing is complete on these samples, they will be used for biomarker analysis. When all study-related testing is complete, the samples will be destroyed.

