##### *Post Dose 2 or 3:*

- 30 ± 10 minutes, and 1 ± 0.25, 2 ± 0.25, 4 ± 1, 8 ± 2, and 12 ± 2 hours post initiation of dosing
- Urine samples for PK will be collected for 12 hours starting immediately after administration of dose 2 or 3

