**Visit 2*****Post Last Dose:***

- 36 ± 12 hours post initiation of last dose

Subjects will be divided into 2 groups (Group A or B) based on randomization for a sparse PK sampling plan. The group assignment will determine the sampling time for each subject. Each subject will have 9 samples of 3 mL blood drawn per sample; and each subject will have urine collected. Biomarker testing will be done on the plasma remaining from sparse PK samples.

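### Section 8.2.5 defines Cmax, tmax and Cmin as observed values, but the sparse schedule cannot observe the loading-dose peak and ties the recorded peak to sampling group and treatment duration

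*Protocol*

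**What the plan says.** Section 8.2.5 plans a final population PK analysis and lists the parameters to be estimated. Clearance, the two volumes and the rate constants are model quantities. In the same list Cmax is "Maximum observed drug concentration", Cmin is the corresponding observed minimum, and tmax is "Time of the maximum drug concentration (obtained without interpolation"). None of the three is tied to a dose.

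Section 6.4 describes plasma samples before the first dose and "at 14 different timepoints following the start of the first dose for a total of 15". It adds: "Each subject will be sampled 9 times from a pre-determined subset of the complete collection of timepoints". Assignment is random: "Subjects will be divided into 2 groups (Group A or B) based on randomization for a sparse PK sampling plan", and "The group assignment will determine the sampling time for each subject".

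After dose 2 or 3 the nominal times are "30 ± 10 minutes, and 1 ± 0.25, 2 ± 0.25, 4 ± 1, 8 ± 2" and 12 hours. A second post-dose set follows dose 6 or 7, only for subjects still receiving drug. The synopsis describes the PK endpoint as "Parameters as compared to data from previous human studies" and names Cmax and tmax among the parameters to be calculated.

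**The concern.** Observed-maximum definitions suit rich sampling around the peak. Here the infusion lasts 20 minutes (section 5.1.2), and median tmax in healthy adults was 0.341 to 0.417 h (section 1.7.2). The earliest post-dose sample is nominally at 30 minutes, each group has only one such sample, and neither follows the loading dose. Under the written rule, part of what is reported as Cmax and tmax would therefore be the sampling assignment. In Group B it would also be how long the subject stayed on drug, which depends on resolution of the crisis because dosing stops at resolution (section 5.1.3). The definitions also sit awkwardly with the model-based analysis in the same section, so two analysts could report different numbers from the same data.

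**Working it through.** **Schedule (Tables 8 and 9).**
- Group A: pre-load; 30 min, 2 h and 8 h after dose 2/3; pre-dose 4/5; pre-dose 6/7; 1 h and 4 h after dose 6/7; Visit 2. Total 9.
- Group B: pre-load; 1 h, 4 h and 12 h after dose 2/3; pre-dose 4/5; 30 min, 2 h and 8 h after dose 6/7; Visit 2. Total 9.
- The union is 15 timepoints, so the protocol's 9 of 15 reproduces. No sample lies between the pre-load draw and dose 2/3.

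**Model inputs.** A 20-minute infusion, 40 mg/kg then 20 mg/kg every 12 h. V2 = 64.2 mL/kg and CLD2 = 31.6 mL/h/kg come from Table 4. Clearance in crisis comes from Table 5 (20/10 regimen, steady state): 20,000 µg/kg per day / 767 = 26.1 mL/h/kg. V1 in crisis is not given. I used 120 mL/kg (Table 4) and 95 mL/kg, the latter chosen to match Table 5.

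**Formula.** With k10 = CL/V1, k12 = CLD2/V1 and k21 = CLD2/V2, α and β satisfy α + β = k10 + k12 + k21 and αβ = k10·k21. The coefficients are A = (α − k21)/[(α − β)V1] and B = (k21 − β)/[(α − β)V1]. A dose D over T = 1/3 h, at time u after its start, contributes Σ (D/T)(c/λ)[1 − exp(−λ·min(u,T))]·exp(−λ·max(u−T,0)) over (c,λ) = (A,α), (B,β). Contributions are summed over doses.

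**Results (µg/mL, nominal times).**

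| | V1 = 95 | V1 = 120 |
|---|---|---|
| Loading-dose peak | 382 | 309 |
| Steady-state peak | 211 | 178 |
| Group A, 30 min after dose 2 / 3 | 206 / 196 | 179 / 169 |
| Group B, 1 h after dose 2 / 3 | 164 / 155 | 150 / 141 |
| Group B, 30 min after dose 6/7 | 193 | 166 |
| Steady-state trough | 21 | 24 |
| 36 h after start of last dose | 0.7 | 1.2 |

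At V1 = 95 the peaks match Table 5 (380 and 210), and the trough is close to the 21.4 modelled in section 1.7.3.

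**Group effect.**
- Group B stopping before dose 6/7, same dose number: 164/206 = 0.80, 155/196 = 0.79, 150/179 = 0.84, 141/169 = 0.83. That is 16 to 21% below Group A, with nominal tmax 1 h against 0.5 h.
- Group B reaching dose 6/7: 193/206 = 0.94, 193/196 = 0.98, 166/179 = 0.93, 166/169 = 0.98. That is at most about 7% below Group A.
- The 30-minute sample against the steady-state peak: 193/211 and 166/178, about 7 to 8% low.

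**How many stop early.** Section 8.3.2 gives 103 h × (1 − 0.438) = 57.9 h for active subjects, SD 60 h. Dose 6 is planned at (6 − 1) × 12 = 60 h. The chance of being unresolved at 60 h is 0.49 for a normal distribution (z = (60 − 57.9)/60 = 0.035), exp(−60/57.9) = 0.35 for an exponential, 0.35 for a gamma and 0.32 for a lognormal. So about 51 to 68% would have resolved before dose 6.

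**Cmin.** The smallest observed value would be the pre-load sample (no drug; earlier exposure is excluded) or the Visit 2 sample, about 1 µg/mL, against a dosing trough of 21 to 24.

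**The case against.** The strongest reply is that these are labels, not methods. Section 6.4 ties sparse sampling to population PK, and section 8.2.5 gives the model the task of comparing with earlier populations and guiding dosing. Table 4 puts the same observed-maximum label on a parameter that its footnote says was estimated from the primary parameters. Table 5 already reports modelled Cmax for this study, Day 1 and steady state separately. That shows what the sponsor probably means, but it does not settle the text. The tmax wording excludes a value predicted between samples, and Table 5 carries Table 4's 167 for study 103 without the asterisk for modelled data.

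A second reply is that the SAP may settle derivations. It may, but the protocol has already fixed definitions that do not fit its schedule.

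Three stronger readings are tempting and are not supported:
- That PK cannot be compared with earlier studies. Clearance, V1, V2, CLD2 and half-life come from the model, and Table 5 has steady-state Cmax for studies 102 and 103.
- That observed Cmax is biased low by about 45%, from 210/380 = 0.55. That ratio mostly reflects a 20 mg/kg against a 40 mg/kg dose.
- That tmax is 1 h throughout Group B. It applies only to those who stop before dose 6 or 7.

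It is also fair that section 1.7.3 sets the dose on Cmin and that both groups have trough samples. No stated dose decision rests on observed Cmax or tmax.

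**Conclusion.** The point holds as a defect of definition. As written, observed Cmax cannot capture the loading-dose peak. In Group B subjects who stop before dose 6 or 7, it reads about 16 to 21% below Group A, with a nominal tmax twice as late. That is roughly half to two thirds of active Group B subjects on the protocol's planning figures. For the rest, the group difference is at most about 7%. Observed Cmin, taken literally, is not a dosing trough.

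These sizes assume V1 of 95 to 120 mL/kg in crisis, nominal sampling times (a sample drawn at the early edge of the 30 ± 10 minute window would coincide with the end of infusion), the protocol's mean and SD for duration, and an assumed distribution shape. The normal end of that range is generous, because a mean of 57.9 h with an SD of 60 h implies negative durations. PK is a secondary objective, and the primary efficacy test is not touched.

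**What to change.** In section 8.2.5, define Cmax, tmax and Cmin as individual predictions from the planned population PK model, each for a named dose: the loading dose and steady-state maintenance separately, as Table 5 already does. Present observed values only as listings by sampling group and dose number, and do not compare observed maxima with earlier studies' Day 1 values. This costs a wording change: no extra blood draws, and the model is already planned. The downside is that the three parameters become model-dependent, and the loading-dose peak will rest on extrapolation, since no sample in this study informs it directly. The report should say so.
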